## **2-5 Ethical approval**

Ethical approval for this study was obtained from the Ministry of Health, Anbar Health Directorate, and the Al-Anbar Cancer Centre, Iraq (Approval No. 1060, dated January 28, 2025).

For any further inquiries, the ethical committee can be contacted via the official email: [[contact]](mailto:[contact]).

The study was conducted by the ethical standards of the Declaration of Helsinki.

## **2-6 Data Analysis**

Data was analyzed using IBM SPSS Statistics version 26. Descriptive statistics (mean, standard deviation, frequency, and percentage) were used to summarize demographic and clinical variables. The Kolmogorov-Smirnov test was applied to assess the normality of continuous variables, and due to non-normal distribution, non-parametric tests were used.

Bivariate analyses included Spearman's correlation coefficient to evaluate associations between psychological outcomes (depression, anxiety, stress) and continuous predictors such as sleep quality, cost, and number of children. The Kruskal-Wallis H test was employed to examine differences in distress levels across cancer stages.

Categorical associations were evaluated using Pearson's Chi-square test. Binary logistic regression analysis was conducted to identify predictors of severe anxiety. Additionally, multivariate linear regression models were constructed for each psychological outcome (PHQ-9, GAD-7, stress), and multicollinearity was assessed using the Variance Inflation Factor(VIF).

Receiver Operating Characteristic (ROC) curve analysis was used to assess the predictive accuracy of stress scores for severe anxiety, with Area Under the Curve (AUC) interpreted based on conventional thresholds. Conceptual path modeling was used to explore potential indirect relationships between stress and anxiety, mediated by sleep disturbance and impaired daily performance.

All tests were two-tailed, and a p-value of less than 0.05 was considered statistically significant.

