### **2-3 Sample Size Calculation**

The sample size was calculated using the standard formula for cross-sectional studies, with the following parameters: a 95% confidence level, a 5% margin of error, and an expected prevalence of psychological distress of 50% to yield the largest possible sample size. Based on these assumptions, the minimum required sample size was estimated to be 384 participants. To enhance the statistical power and compensate for potential non-response or incomplete data, a larger sample was targeted. Consequently, a total of 500 breast cancer patients were enrolled in the final analysis, exceeding the minimum requirement.

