### **2-4 Questionnaire tool and data extraction**

Patients' data were collected from medical records (demographics data, medication use history, and clinical profile). Cost data was obtained from the finance department at the center. Financial data included all available direct medical costs, such as treatment and physician visits. Moreover, patients were contacted to estimate the indirect cost associated with breast cancer therapy. A validated assessment tool, the Generalized Anxiety Disorder 7-item (GAD-7) and the Patient Health Questionnaire (PHQ-9) were used to assess anxiety and depression [Spitzer et al., 2006; Kroenke et al., 2001]. The patients were asked to determine the degree of applicability of each item (question) on a 4-point Likert scale. The participants' responses varied from 0 to 3, with 0 denoting "Not at all" and 3 denoting "Nearly every day." Nine elements comprise the PHQ-9 instrument. Items are scored on a scale of 0 to 3, resulting in a total score that ranges from 0 to 27. A total score of 0–4 indicates minimal depression, 5–9 mild depression, 10–14 moderate depression, 15–19 moderately severe depression, and 20–27 severe depression. Seven elements comprise the

GAD-7 instrument. Items are scored on a scale of 0 to 3, resulting in a total score that ranges from 0 to 21. Mild anxiety is indicated by a total score of 5–9, moderate anxiety by 10–14, and severe anxiety by 15–21.

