### 3 - Results

A total of 500 breast cancer patients were included in the final analysis. Descriptive statistics revealed a high prevalence of psychological distress within the sample, with elevated scores in depression, anxiety, and stress domains.

Spearman correlation analysis revealed strong positive associations between sleep difficulty and psychological outcomes: depression ( $r = 0.85$ ), anxiety ( $r = 0.77$ ), and stress ( $r = 0.85$ ), all statistically significant at  $p < 0.001$ . Use of sedatives was also significantly correlated with elevated distress scores ( $r > 0.90$  across models).

Kruskal-Wallis tests demonstrated statistically significant differences in mean ranks of depression, anxiety, and stress across cancer stages ( $p < 0.01$ ), with higher distress in patients with advanced-stage disease.

Multivariate linear regression identified the following as significant predictors of psychological distress:

- PHQ9\_Total:  $\beta = 0.42$ ,  $p < 0.001$
- Anger:  $\beta = 2.08$ ,  $p < 0.001$
- Cancer Stage:  $\beta = 0.92$ ,  $p = 0.0014$

Psychological support was not a significant predictor ( $p = 0.606$ ).

Binary logistic regression showed that PHQ9 and anger significantly predicted severe anxiety, with odds ratios of 1.32 and 1.27, respectively ( $p < 0.001$ ). Stage of disease also emerged as a significant factor in anxiety prediction.

Receiver Operating Characteristic (ROC) curve analysis yielded an Area Under the Curve (AUC) of 0.74 for stress in predicting severe anxiety, indicating a fair level of discriminative ability.

Finally, conceptual path analysis demonstrated that the relationship between stress and anxiety was primarily indirect, mediated through sleep disturbance and daily performance impairment. The direct path from stress to anxiety was negligible ( $r = -0.01$ ), suggesting a mediated mechanism of action.

**Table 1.** Descriptive Statistics of Study Variables

Variable	N	Minimum	Maximum	Mean	SD
Total Cost	500	80	34785	3721.69	4456.79
PHQ9_Total	500	1	27	17.99	6.11
GAD7_Total	500	1	21	12.79	3.81
Cancer Stage	500	0	4	2.52	1.09
Children	500	0	5	2.53	1.63
Metastatic	500	0	1	0.36	0.48
Stress Level	500	0	4	2.64	0.79

The descriptive characteristics of the study variables are presented in **Table 1**. Depression and anxiety scores were moderately high, while stress levels were also elevated. Treatment cost showed substantial variability across participants.

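### Anger, cancer stage and psychological support enter the tabulated adjusted models only for severe anxiety yes/no, although the full GAD-7 score is available for all 500 patients

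*Combined protocol and SAP*

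**What the plan says.** Section 2-4 grades the GAD-7 total, which runs from 0 to 21: "Mild anxiety is indicated by a total score of 5–9, moderate anxiety by 10–14, and severe anxiety by 15–21". Table 1 gives the row "GAD7_Total 500 1 21 12.79 3.81" (variable, N, minimum, maximum, mean, SD), so the total is held for every patient analysed.

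Section 2-6 plans several analyses of anxiety:

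- **Binary.** "Binary logistic regression analysis was conducted to identify predictors of severe anxiety". Tables 5 and 6 report these models. Both contain PHQ-9, anger, psychological support and cancer stage; Table 5 also contains stress level.
- **Linear.** A linear model is planned for each psychological outcome, GAD-7 included. The GAD-7 block of Table 4 lists sedative use, sleep-related worry, sleep satisfaction, children, total cost and metastatic status. It does not list anger, stage or support.
- **Unadjusted.** Kruskal-Wallis tests across stages are planned. Table 3 reports H = 19.705 on 3 df for the GAD-7 total.

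The text describes results on the score scale. The Results present 0.42 (PHQ-9), 2.08 (anger) and 0.92 (stage) as coefficients from linear regression. The Discussion says that stage predicted higher anxiety scores (0.92), and that PHQ-9 and anger were the leading predictors in linear as well as logistic models (0.42 and 2.08). All three values are the coefficients of Table 6, which is labelled logistic.

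**The concern.** With a cut at 15, scores of 1 and 14 count as the same outcome, and 14 and 15 as opposite outcomes. Any relation between a predictor and anxiety within the 1–14 range or the 15–21 range is lost, and the estimates are less precise than the data allow. The Discussion interprets all three predictors, and for none of them do the tables give an adjusted estimate on the full score.

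Two things are at stake. The first is precision for psychological support. The Discussion explains its null result by limited or under-used services and still draws a message from the direction of the effect. The second is that a reader who takes the Results text at face value would read 2.08 as GAD-7 points per unit of anger. In Table 6 it is a log-odds, that is, an odds ratio of about exp(2.08) = 8.0.

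**Working it through.** **The plan's own figure.** The only design calculation is for a single prevalence: "a 95% confidence level, a 5% margin of error, and an expected prevalence of psychological distress of 50" percent. n = 1.96² × 0.5 × 0.5 / 0.05² = 384.16, which agrees with "the minimum required sample size was estimated to be 384 participants". It says nothing about the severe-anxiety models, and no power or precision figure is given for them.

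**Inputs.** GAD-7 mean 12.79, SD 3.81, N = 500 (Table 1); severe = 15 or more (section 2-4; section 2-6 does not repeat the cut, so I take that definition); Spearman correlation of PHQ-9 with GAD-7 0.79 (Table 2). Assumptions: an approximately normal score, and a severe share implied by that mean and SD, since the documents do not report it.

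**Step 1: information kept without adjustment.** For a small shift in a normal score, a binary cut keeps φ(k)² / [p(1 − p)] of the information, where k = (cut − 12.79)/3.81 and p is the share above the cut.

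| Cut | k | p | φ(k) | Information kept | Equivalent N of 500 | CI width ratio |
|---|---|---|---|---|---|---|
| 14.5 (continuity) | 0.449 | 0.327 | 0.361 | 0.591 | 296 | 1/√0.591 = 1.30 |
| 15 | 0.580 | 0.281 | 0.337 | 0.563 | 281 | 1/√0.563 = 1.33 |

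If the severe share were 20%, 0.490 would be kept; at 50%, 0.637. A normal score made discrete and truncated to 1–21, with the mean and SD matched, gives a severe share of 33.8% and 0.604 kept. A logistic-shaped score gives 0.638 (cut 14.5) and 0.575 (cut 15).

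**Step 2: information kept after adjusting for PHQ-9.** Tables 5 and 6 include PHQ-9, so Step 1 does not describe those models exactly. Treat 0.79 as a normal correlation, let X be the standardised PHQ-9 and u = (k − 0.79X)/√(1 − 0.79²). For a predictor unrelated to PHQ-9, the fraction kept is the average over X of φ(u)² / {Φ(u)[1 − Φ(u)]}. This gives 0.386 at a cut of 14.5 and 0.363 at 15. Intervals are then about 1.61 and 1.66 times as wide as they need be.

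**Step 3: the three predictors in Table 6.**

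- Anger (2.08, p < 0.001) and stage (0.92, p = 0.0014) are significant despite the cut.
- Support: −0.18, interval −0.84 to 0.49. As an odds ratio this is exp(−0.84) = 0.43 to exp(0.49) = 1.63. Table 5 gives 0.54, and ln 0.54 = −0.62 lies inside the interval, as does 0.
- If support kept the same standardised effect on the full score, its z of −0.52 would become −0.52/√0.591 = −0.68 (p about 0.50) by Step 1, or −0.52/√0.39 = −0.83 (p about 0.40) by Step 2. It would still be non-significant, but with a narrower interval.

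**Step 4: stage on the full score.** H = 19.705 on 3 df gives p = 0.0002, in line with Table 3. Stage is therefore examined against the uncut score, but without adjustment.

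**The case against.** The strongest reply has four parts.

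1. *The full score is not ignored.* This stands. Stage is tested on it in Table 3, metastatic status is in the linear GAD-7 model of Table 4, and the Discussion reports a correlation of −0.07 between support and anxiety (scale not stated). A reader might infer that all three predictors are examined only against the cut. The documents do not support that; the point is confined to the tabulated adjusted models.

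2. *The disagreement between Tables 5 and 6 has another cause.* This stands too. Stage moves from an odds ratio of 0.61 to a coefficient of +0.92, and support from p = 0.021 to p = 0.606. It is tempting to read this as damage from the cut, but both tables are labelled as models of the same binary outcome. The tables differ in covariates (stress is only in Table 5), Table 6 is called corrected, and the Discussion mentions an adjustment to stage coding. The conflict must be reconciled separately.

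3. *No conclusion changes.* This stands as far as can be shown: Step 3 leaves support non-significant and the other two significant. It limits the weight of the point. It does not remove the gain in precision or the need for the score-level result that the text claims.

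4. *Severe anxiety is a category of the instrument and a fair clinical question, and normality is doubtful.* The first half stands: the cut is not data-driven, it matches the ROC target, and the plan names no main model. That is a reason to keep the logistic model, not to leave out the other. The second half means that the percentages are approximations.

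**Conclusion.** The concern holds in limited form. In the tabulated adjusted models, anger, stage and support are related to anxiety only through a yes/no cut, while a 0–21 score is available for everyone and already has an adjusted model that leaves them out. Under approximate normality the cut keeps about 56–59% of the information without adjustment (49–64% for severe shares of 20–50%) and about 36–39% with PHQ-9 in the model. These figures rest on a distribution that section 2-6 itself questions and on a severe share that is not reported.

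The practical consequence falls mainly on psychological support, for which the present interval cannot separate no effect from the effect in Table 5. The missing model is also the one that the text describes: the values offered as linear results and as effects on anxiety scores are Table 6 logistic coefficients. This is a cheap improvement in precision and a correction to reporting, not a demonstration that a finding is wrong.

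**What to change.** - Add a regression of GAD-7 total on PHQ-9, anger, psychological support and cancer stage, either linear with robust standard errors or ordinal. Both suit a bounded score reported as non-normal.
- Report it alongside the severe-anxiety logistic model, state the cut of 15 in section 2-6, and give the number of severe cases.
- Base statements about anxiety scores and linear regression in the Results and Discussion on the new model, and label 0.42, 2.08 and 0.92 as log-odds from Table 6.
- Identify the added model as introduced after the results were known.

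The cost is one model on data already held. Readers will see effects in GAD-7 points as well as odds ratios. The new model does not settle the conflict over stage and support between Tables 5 and 6, which needs its own correction.

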**Table 2.** Spearman Correlation Matrix Among Study Variables

Variable	PHQ9_Total	GAD7_Total	Stress Level	Sleep Difficulty	Sleep Satisfaction	Total Cost

PHQ9_Total	1.00	0.79	0.66	0.85	0.49	-0.11
GAD7_Total	0.79	1.00	0.65	0.77	0.62	-0.10
Stress Level	0.66	0.65	1.00	0.85	0.55	-0.12
Sleep Difficulty	0.85	0.77	0.85	1.00	0.48	-0.08
Sleep Satisfaction	0.49	0.62	0.55	0.48	1.00	-0.09
Total Cost	-0.11	-0.10	-0.12	-0.08	-0.09	1.00

[figure not shown]
Spearman correlation coefficients between psychological outcomes and sleep-related variables are shown in **Table 2**. Strong positive correlations were observed between depression, anxiety, stress, and sleep difficulty.

**Table 3.** Kruskal–Wallis Test for Differences Across Cancer Stages

Variable	Chi-square (H)	df	P-value
Stress Level	31.092	3	<0.001
PHQ9_Total	14.762	3	0.002
GAD7_Total	19.705	3	<0.001

The Kruskal–Wallis test results (**Table 3**) indicate significant differences in depression, anxiety, and stress levels across cancer stages ( $P < 0.05$ ).

**Figure 1.** Chi-square (H) Values for Stress, Depression, and Anxiety

**Figure 1** shows the Chi-square (H) values for stress, depression, and anxiety. Stress exhibited the highest value (H = 31.09), followed by anxiety (H = 19.71) and depression (H = 14.76), all indicating significant differences across groups ( $P < 0.05$ ).

**Table 4.** Multiple Regression Analysis of Factors Associated with Depression, Anxiety, and Stress among Patients

Outcome	Predictor	B	T	P-value	VIF	R 
Depression (PHQ-9)	Use of Sedatives	4.842	10.817	<0.001	1.766	0.702
	Sleep Difficulty	4.52	11.221	<0.001	4.866	
	Sleep Satisfaction	0.364	2.01	0.045	1.021	
	Children	0.075	0.626	0.532	1.039	
	Total Cost	7.5E-5	2.209	0.028	1.022	

	Metastatic	-0.13	-0.408	0.684	1.048	
Anxiety (GAD7)	Use of Sedatives	4.064	12.807	<0.001	1.766	0.615
	Sleep-related Worry	1.521	6.193	<0.001	3.655	
	Sleep Satisfaction	0.539	1.886	0.060	4.866	
	Children	0.205	1.889	0.060	1.039	
	Total Cost	3.0E-5	1.246	0.213	1.022	
	Metastatic	0.203	0.896	0.371	1.048	
Stress Level	Use of Sedatives	1.856	29.413	<0.001	1.766	—
	Sleep-related Worry	0.149	3.048	0.002	3.655	
	Children	0.037	1.705	0.089	1.039	
	Metastatic	0.084	1.865	0.063	1.048	
	Total Cost	3.4E-6	0.711	0.477	1.022	

The results of the multiple regression analysis are summarized in **Table 4**. Use of sedatives and sleep-related worry were significant predictors of stress, depression, and anxiety scores.

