Although anger remains an underexplored emotional construct in oncology, its relevance is gaining traction. In Iraq, sociocultural norms that discourage emotional expression, combined with the psychological toll of cancer, may intensify internalized anger, contributing to emotional dysregulation. This perspective is supported by findings from the national report, which highlighted elevated psychological distress among cancer patients and emphasized the role of suppressed emotions in shaping anxiety and avoidance behaviors (20).

These findings emphasize the significance of addressing emotional dysregulation, particularly in patients presenting with overlapping symptoms of depression and anxiety.

This suggests that psychological screening tools should incorporate anger-related items to facilitate the early identification of high-risk cases.

The conceptual path model derived from the dataset suggests that stress influences anxiety primarily through indirect mechanisms, notably sleep disturbance and impaired daily functioning. While the direct association between stress and anxiety was minimal ( $r = -0.01$ ), robust indirect effects were observed via sleep problems ( $r = 0.74$ ) and functional impairment ( $r = 0.77$ ). These findings are consistent with regional studies from Egypt and Oman, highlighting sleep disturbance and fatigue as key mediators of psychological distress in oncology patients. (Al-Habsi et al., 2021; Gabra & Hashem, 2021; Hendy et al., 2025).

This structure reinforces theoretical frameworks such as the Transactional Model of Stress and Coping, where maladaptive emotional responses (e.g., stress) translate into clinical outcomes (e.g., anxiety) through sleep and functional capacity mediators. Similar models have been proposed in Jordanian studies (24). Though the present model uniquely incorporates performance and anger as variables of interest, adding depth to the psychosocial profile.

The inclusion of psychological support and its weak inverse association with anxiety ( $r = -0.07$ ) further suggests that strengthening emotional resources could buffer the transition from stress to anxiety. This model may therefore serve as a foundational structure for targeted interventions in Iraqi cancer care systems, particularly in resource-limited settings.

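### No description of the stress–anxiety path model includes depression, and the size of the claimed sleep pathway depends on the role depression is given

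*Combined protocol and SAP*

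**What the plan says.** Section 2-6 (Data Analysis) gives the method: "Conceptual path modeling was used to explore potential indirect relationships between stress and anxiety, mediated by sleep disturbance and impaired daily performance". Section 3 (Results) reports that "conceptual path analysis demonstrated that the relationship between stress and anxiety was primarily indirect, mediated through sleep disturbance and daily performance impairment". It adds "The direct path from stress to anxiety was negligible ( $r = -0.01" and infers a mediated mechanism from this. The Figure 3 legend repeats the same structure of stress, sleep, daily functioning and anxiety.

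Section 4 (Discussion) widens the description: "Though the present model uniquely incorporates performance and anger as variables of interest". It also mentions psychological support, gives 0.74 for the sleep route and 0.77 for the functional route, and offers the model as a basis for interventions.

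None of these descriptions names depression. Elsewhere depression is prominent. Table 1 gives a PHQ-9 total for all 500 patients, and Tables 5 and 6 use PHQ-9 to predict severe anxiety. The Discussion ranks depression and anger as the leading independent predictors of severe anxiety. The GAD-7 row of Table 2 reads "GAD7_Total 0.79 1.00 0.65 0.77 0.62 -0.10", with PHQ-9 in the first column. The PHQ-9 row reads "PHQ9_Total 1.00 0.79 0.66 0.85 0.49 -0.11".

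**The concern.** A mediation claim rests on what the outcome equation conditions on. Depression is strongly related to all three of stress (0.66), sleep difficulty (0.85) and anxiety (0.79). If it is left out, the sleep coefficient contains whatever sleep and depression share in relation to anxiety. The reader cannot tell how much of the pathway belongs to sleep.

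At stake is one of the report's main conclusions: that stress reaches anxiety mainly through sleep and daily performance, with almost nothing direct. The Discussion builds intervention advice on it, so it should be shown whether it survives the inclusion of a variable the study already holds.

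**Working it through.** **Inputs.** These are Spearman correlations from Table 2, with N = 500 from Table 1. Stress–sleep difficulty 0.85; stress–PHQ-9 0.66; sleep difficulty–PHQ-9 0.85; GAD-7 with stress 0.65, with sleep difficulty 0.77, with PHQ-9 0.79. Daily performance and anger are not in Table 2, so the documented model cannot be rebuilt. What follows is a surrogate with sleep difficulty as the only mediator from the plan.

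**Step 1: the printed direct path.** Partial correlation of stress and anxiety given sleep difficulty:

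(0.65 - 0.85 × 0.77) / √[(1 - 0.85²)(1 - 0.77²)] = -0.0045 / 0.336 = -0.013, which agrees with the printed -0.01.

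**Step 2: standardised paths without PHQ-9.**
- Direct: (0.65 - 0.85 × 0.77) / (1 - 0.85²) = -0.0045 / 0.2775 = -0.016
- Sleep to anxiety: (0.77 - 0.85 × 0.65) / 0.2775 = 0.784
- Carried by sleep: 0.85 × 0.784 = 0.666; R² = 0.593

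**Step 3: PHQ-9 added to the anxiety equation.** Solving b = R⁻¹r for the three predictors:

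| Path to anxiety | Without PHQ-9 | With PHQ-9 | SE | t |
|---|---|---|---|---|
| Stress (direct) | -0.016 | 0.099 | 0.051 | 1.94 |
| Sleep difficulty | 0.784 | 0.252 | 0.073 | 3.47 |
| PHQ-9 | – | 0.511 | 0.051 | 10.03 |

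R² rises to 0.662. The sleep path falls by 1 - 0.252/0.784 = 68%. The direct path has p about 0.053 and a normal-theory 95% CI of -0.001 to 0.199. The variance inflation factor for sleep difficulty is 7.7.

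**Step 4: what sleep carries under each role for depression.** The anxiety equation of Step 3 is the same in all three.
- *Downstream of sleep.* PHQ-9 on stress and sleep gives stress (0.66 - 0.85²)/0.2775 = -0.225 and sleep (0.85 - 0.85 × 0.66)/0.2775 = 1.041. Carried by sleep: 0.85 × (0.252 + 1.041 × 0.511) = 0.666. The route through PHQ-9 that bypasses sleep is -0.225 × 0.511 = -0.115, and direct is 0.099. Total 0.65.
- *Parallel path.* Sleep 0.85 × 0.252 = 0.214; depression 0.66 × 0.511 = 0.337; direct 0.099. Total 0.65.
- *Upstream.* Stress to sleep, adjusted for PHQ-9, is (0.85 - 0.85 × 0.66)/(1 - 0.66²) = 0.512. Carried by sleep: 0.512 × 0.252 = 0.129. The adjusted total is 0.129 + 0.099 = 0.228.

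**Step 5: robustness.** Over all ±0.005 rounding corners of the six correlations, the cut in the sleep path is 57% to 82% and the direct path is 0.033 to 0.165. A parametric bootstrap (multivariate normal, N = 500) gives 95% intervals of 53% to 85% for the cut and 0.002 to 0.196 for the direct path. If Sleep Satisfaction is also entered, adding PHQ-9 moves the direct path from -0.202 to -0.084 and sleep difficulty from 0.767 to 0.374 (-51%). That specification does not return the printed -0.01.

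**The case against.** The strongest reply is that conditioning on depression may be wrong. The only model in the report that relates the two runs from sleep to depression: Table 4 regresses PHQ-9 on sleep difficulty. If that order is right, adjustment removes part of the very effect being studied, and Step 4 shows that sleep's share stays at 0.67. This stands. A reader might infer that depression is a confounder and that the sleep path merely absorbs it; the data do not show that. But the reply does not rescue the claim, because nothing in a cross-sectional design favours that order over the other two.

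A reader might also infer that adjustment turns the direct path positive. That is not established. The estimate is not significant at the plan's 0.05, the normal-theory and bootstrap intervals fall on either side of zero by a hair, and the sign is negative if Sleep Satisfaction is entered. With PHQ-9 downstream or parallel, 0.10 of 0.65 is direct, so a mainly indirect association survives; what is unsettled is how much of it is sleep.

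Finally, the omission itself is inferred. The descriptions are not exhaustive, since anger and support appear only in the Discussion. Figure 3 was not visible in the text reviewed. The agreement in Step 1 is a single two-decimal match from a model without daily performance, and the surrogate yields 0.784 or 0.666 for sleep, neither equal to the Discussion's 0.74. The match suggests, but cannot prove, that depression was not controlled.

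**Conclusion.** The point holds as one of sensitivity, not of demonstrated confounding. In the surrogate, the sleep coefficient falls by about two thirds when PHQ-9 enters, and that fall is robust to rounding and sampling error. Sleep's share of the stress–anxiety association is 0.67, 0.21 or 0.13 (the last out of an adjusted 0.23) according to an ordering these data cannot settle. The report's statement that path analysis demonstrated mediation through sleep is therefore stronger than its evidence.

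This assumes that Table 2 is correct as printed, that rank correlations can be treated as linear, that sleep difficulty stands for sleep disturbance, and that daily performance and anger, which could not be included, would not remove the sensitivity. Figure 3 should be checked for depression. If it is already in the fitted model, the remedy reduces to saying so and stating the assumed order.

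**What to change.** Keep the present path model and list every variable in it. Add a sensitivity refit on the patient-level data, including daily performance and anger, with PHQ-9 entered in turn as a covariate (upstream), as a parallel mediator, and as downstream of sleep. Report each path with a bootstrap confidence interval.

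In the Results, replace the statement that mediation was demonstrated and the inference of a mediated mechanism. Say instead that the association is consistent with a sleep pathway, but that its size depends on the assumed role of concurrent depression and cannot be separated from it in these data. Carry the same caution into the Discussion where the model is offered as a basis for interventions.

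The cost is a small amount of further analysis, with no new data, and a weaker mediation statement.
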